8.2.6 Unscheduled Visits

Visit windows are defined in the protocol and SOE. For a visit not performed within the window period, the interim visit will be completed and documented as a protocol deviation. If there is a missed visit that requires safety assessments or local safety labs,

study staff should attempt to bring the participant in for an interim visit as soon as possible. Safety evaluations should be completed per SOE for the missed visit.

Should a participant require an unscheduled visit between visits, procedures performed at these visits are usually toxicity/safety assessments (including local safety labs). The procedures completed at the unscheduled visit should be performed only if clinically indicated.

8.2.7 Vaccine or Placebo Administration Visit:

Vaccine (**M3** or **M4** or **M3+M4**) or placebo injections are given at Day 0.

1. Complete required pre-vaccine/placebo assessments and blood draws (per SOE) prior to the administration of the vaccine/placebo.
2. Record the RID and the vaccine/placebo injection, including dose, and time of administration. Record where the injection was given (location). If unable to administer the entire dose for any reason, notify the study PI (or designee) and document the reason.
3. Complete the following:
 - During administration of the vaccines, medicines and resuscitation equipment will be immediately available for the management of anaphylaxis.
 - Two licensed staff will verify and confirm the vaccine/placebo for administration.
 - Two licensed staff will confirm the research chart PID /SID to the PID/SID on the blinded study treatment label.
 - Document the verification process.
 - Have participant seated in a secure chair prior to injection to avoid the risk of fall due to possible dizziness/lightheadedness, or in rare cases, syncope.
 - Administer vaccine/placebo as a single IM injection in the deltoid muscle, preferably in the non-dominant arm, unless a participant requests vaccination in their dominant arm.
 - The study DOES NOT ALLOW any modifications to any vaccine doses.
 - Study staff will wear gloves and eye protection when handling the vaccine/placebo product.

8.2.8 Post Vaccination/Injection Management:

1. Observe participant and injection site for 60 minutes following each vaccine/placebo injection for clinical AEs.
 - Assess for injection site reaction every 15 minutes × 4, document observed reactions
 - Observe and assist participant when coming to a standing position for the first time following each administration of vaccine/placebo
 - Obtain vital signs (BP, P, RR, and T) prior to discharge home
2. Instruct participant to contact the study coordinator immediately with any concerns about the injection site after leaving the clinic.
3. Provide post vaccination symptom log and instructions for completion prior to leaving the clinic.
 - Review symptom log at the Day 2 and Day 7 visits following the vaccination
 - Symptom logs are collected at the Day 7 visit
4. Contact participant the day after the injection in the manner pre-determined by the study coordinator and participant.
 - Assess for signs and symptoms resulting from vaccine or placebo administration
5. Following receipt of vaccine/placebo, participants will be followed with study visits through Day 70 and the Days 84 and 168 visits will be completed via phone contact.
6. Participants will be contacted by phone at Days 84 and 168 to assess for and document new adverse events.
7. If the participant reports any AEs possibly related to treatment at either the Day 84 or Day 168 assessments, an additional unscheduled visit may be needed to further evaluate the participant and attribution to treatment.

8.2.9 Post Vaccination Symptom Log

Participants will be given a “Post vaccination symptom log” to use as a memory aid for tracking adverse events that occur during the 3 days following the injection. Participants will record daily temperature and systemic symptoms.

1. For this study, solicited AEs occurring during the 3 days after the vaccine/placebo injection will include:
 - unusually tired/feeling unwell
 - muscles aches
 - headache
 - chills
 - nausea
 - joint pain
2. Instruct participants to take their temperature at least once daily, starting with the day of injection (Day 0), after leaving the clinic and through Day 3 post-injection.
3. Temperature should be taken orally in the evening whenever possible. If more than one measurement is made in a day (for example due to feeling unwell), then the highest temperature taken that day should be recorded.
4. The symptoms and assignment of grades will be reviewed with participants to assure an understanding of how to use and evaluate each symptom during these first 3 days.

The study coordinator will discuss the symptom logs for accuracy and completeness at Day 2 and review and collect the completed symptom log at the Day 7 Visit. The study coordinator will review symptoms with participants for each identified symptom and clarify the grading assigned at the time. Additionally, active solicitation of AEs will be done at every visit. Participants will also be asked to contact the study coordinator, study PI, or designee should they experience any adverse events at any time points during the study.

8.2.10 *Solicited AE Assessments:*

The study coordinator will assess for Solicited AEs (expected) symptoms at Day 2 and Day 7 following each injection.

Assessments will consist of a standard series of questions administered at approximately 48 hours post vaccination (Day 2) and at the Day 7 Visit. The following local reaction evaluations ([Table 9](#)) and systemic reaction evaluations ([Table 10](#)) are part of each assessment.

Table 9 Local Reaction Solicited AE Assessments

Injection site erythema (redness)	Injection site pruritus (itching)
Injection site tenderness	Injection site swelling

Warmth at injection site	Skin discoloration
Injection site pain	Skin damage (vesiculation or ulceration)
Induration (hardening or formation of a crust or scab)	

Table 10 Systemic Reaction Solicited AE Assessments

Vomiting	Fatigue (extreme tiredness)
Malaise	Headache
Flu like symptoms	Temperature (fever $>37.7^{\circ}\text{C}$ or 99.9°F)
Sweating	Chills
Diarrhea	Nausea
Dizziness	Myalgia (muscle pain)
Anorexia	Abdominal pain
Syncope	

Study staff will follow new or unresolved vaccine-related AEs to resolution. In general, participants self-reporting any post-injection reaction greater than mild are to be evaluated by the study PI (or designee) within 72 hours after onset, unless the reaction is improving and/or has completely resolved.

Institute appropriate countermeasures, including medical intervention or procedures, if clinically indicated.

8.2.11 *Laboratory Evaluations*

Details of specimen collection are found in the Lab Procedures Manual for this study.

Labs utilized for processing and resulting the clinical evaluations are the UNC McLendon Lab and LabCorp. The study PI (or designee) assesses the results of all clinical laboratory tests to determine continuing eligibility or AE relatedness at specified visits. Lab results or values outside the normal reference range require the investigator (or designee) to determine if the abnormal value is clinically significant and/or related to a study intervention. All confirmed abnormal laboratory values that the investigator deems clinically significant and/or related to a study intervention must be reported as AEs, regardless of grade. Post-entry laboratory values, Grade ≥ 2 , will be recorded. Participants and/or their primary care provider will be informed of any clinically significant laboratory test result or clinical event that occurs throughout the study. Participants will be referred for care when appropriate.

Hematology: Perform hemoglobin, hematocrit, white blood cell count (WBC), differential WBC, absolute neutrophil count (ANC), and platelet count in real time at the local laboratory.

Note: CBC with differential for Leukapheresis procedures:

- A STAT CBC with differential is required prior to each leukapheresis performed at the UNC Apheresis Lab unless results completed within 24 hours of the procedure are available to the Apheresis Lab performing the procedure.
- Leukapheresis procedures performed at a local apheresis collection center require a CBC within 30 days of procedure.

Liver Function Tests: Perform total bilirubin, AST (SGOT), ALT (SGPT), and alkaline phosphatase in real time at the local laboratory.

NOTE: For participants on ritonavir boosted atazanavir, total and direct bilirubin should be measured.

Blood Chemistries

Screening lab evaluation includes electrolytes (sodium, chloride, potassium, CO₂/bicarbonate), glucose, blood urea nitrogen (BUN), creatinine, calcium, phosphate, albumin, magnesium, LDH, and total protein in real time at the local laboratory.

Safety lab evaluations throughout the study include electrolytes (sodium, potassium, chloride, CO₂/bicarbonate), BUN, creatinine, calcium, magnesium, and glucose (also reference Pre-Vaccine Safety Lab Assessment).

Creatinine and Creatinine Clearance

Creatinine clearance (eGFR) calculations will use the CKD-EPI equation. This calculation can be found at https://www.qxmd.com/calculate/calculator_251/egfr-using-ckd-epi

The creatinine clearance (eGFR) will be required for study enrollment eligibility. The study assesses serum creatinine level at all the safety lab checks and uses the serum creatinine value for toxicity grading and as confirmation to receive vaccine or placebo doses.

The creatinine clearance (eGFR) value reported as part of the lab report of serum creatinine level will be re-assessed and re-calculated if incidental finding indicates a value \geq Grade 3. The re-calculated value using the CKD-EPI equation will be used to determine the severity of the lab abnormality.

Pre-Vaccine Safety Lab Assessments

Participants will have a Pre-Dose Safety Lab Assessment completed at either Visit 2 or the leukapheresis and within the 10 days prior to the vaccine/placebo dosing visit. These safety lab results must be within the eligibility criteria parameters established for this study. Labs that fall outside the parameters can be repeated one time only to qualify the participant to proceed on study.

After repeat testing, any lab value that remains outside the guidelines but considered clinically non-significant and documented as such by the study clinical PI (or designee), must be reviewed and approved by the protocol and/or safety committee prior to the vaccination.

Serum and Point of Care (POCT) Urine Pregnancy Test: A negative serum pregnancy test (to rule out pregnancy) is required on all women at screening, and a negative urine pregnancy test on Day 0, regardless of documented procedures that prohibit pregnancy.

The use of the POCT urine pregnancy test as confirmation of negative pregnancy status is acceptable for vaccination visit at Day 0, unless pregnancy is suspected. If pregnancy is suspected, a serum pregnancy test must be done to rule out pregnancy. The test must be negative within 48 hours of the dose.

In addition, a POCT pregnancy test should be performed at any visit post vaccination, if pregnancy is suspected. Because the study has no direct clinical benefit, this added protection is warranted.

The study will use the date of LMP to rule out suspected pregnancy. Pregnancy will be suspected if >35 days since first day of last menstrual period in pre-menopausal women has elapsed. **Hepatitis Screen:** Both hepatitis tests (HCV AB and HBsAg) must be negative or non-detected to be included on the study. A positive HCV AB test reflexed to Hepatitis C RNA revealing a negative result is acceptable.

Eligibility will be determined based on negative testing, per above definition at screening.

RPR: Complete at screening to rule out clinically active untreated syphilis.

Participant may participate on study following documentation of adequate treatment of syphilis at screening (Visit 1). Participants diagnosed with syphilis at screening, will be referred for and require documentation of treatment. The participant may rescreen following a minimum of 14 days post syphilis treatment.

HIV Ag/Ab Test: Complete HIV testing at screening if documentation of HIV infection is not available from prior records.

Fasting Lipid Panel: Obtain total cholesterol, HDL, LDL calculation, VLDL calculations, and triglycerides at screening.

Prothrombin time (PT), INR, and APTT: Evaluate at the Screening Visit.

Urinalysis: Do dipstick testing (including protein, glucose, hemoglobin, pH, and ketone) at select visits. Do microscopic analysis only in the event of abnormal results from dipstick testing.

Estimated Blood Volumes Associated with Study Visits: Estimated blood volumes associated with each study visit is provided in [Table 11](#).

Table 11 Blood Volumes Associated with Study Visits

Day #	Approximate Blood Volume (mL)	Day #	Approximate Blood Volume (mL)
Screen	100	Day 7	115
Enrollment/Baseline	75	FNA (optional)	3
Leukapheresis	20	Day 14	110
		Day 28	75
		Day 56	100
FNA (optional)	3	Day 70	130
Day 0	85	Day 84	0
Day 2	0	Day 168	0

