2.3 Risk/Benefit Assessment

2.3.1 *Known Potential Risks*

Risks of M3 and M4 vaccines

Based on safety data from studies with earlier generations of the MVA.HIVcons vaccines and other MVA-vectored vaccines, adverse reactions (AEs) to **M3** and **M4** vaccine are anticipated to involve transient Grade 1 and 2 local reactions such as pain or erythema at the injection site in addition to headache, malaise, and fever (IB, MVA.tHIVcons3 version 2.0; IB, MVA.tHIVcons4 version 2.0). There have been no SAEs or SUSARs in several studies of MVA.HIVcons administered in combination with other vaccines (IB, MVA.tHIVcons3 version 2.0; IB, MVA.tHIVcons4 version 2.0).

Clinical trial data with MVA.HIVcons administered by IM injection with 2 $\times 10^8$ pfu indicates that the following AEs may occur in some participants: injection site tenderness, erythema, swelling, pruritus, induration, myalgia, headaches, dizziness, fatigue, fever,

malaise, nausea, chills, vomiting, flu-like symptoms, diarrhea, sweating, anorexia, abdominal pain, and/or syncope.

Standard local (**Error! Reference source not found.**) and systemic reactions (**Table 5**) can occur, with most appearing within the first 24 hours and usually subsiding within 48 – 72 hours.

Table 4 Local Reactions

Injection site erythema (redness)	Injection site pruritus (itching)
Injection site tenderness	Injection site swelling
Warmth at injection site	Skin discoloration
Injection site pain	Skin damage (vesiculation or ulceration)
Induration (hardening or formation of a crust or scab)	

Table 5 Systemic Reactions

Vomiting	Fatigue (extreme tiredness)
Malaise	Headache
Flu like symptoms	Temperature (fever >37.7°C or 99.9°F)
Sweating	Chills
Diarrhea	Abdominal pain
Dizziness	Myalgia (muscle pain)
Anorexia	Nausea
Syncope	

The expectation is that these AEs will be primarily mild in severity; however, occasional moderate or severe AEs (local pain, headache, malaise, diarrhea, myalgia) have occurred in other vaccine studies with MVA.HIVcons.

Due to lack of experience in humans, there is no information available about the relationship of AEs to the administration of **M3** or **M4** vaccines.

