6.4 Study Intervention Compliance

Participants will keep a daily diary of solicited AEs for both local and systemic symptoms for 3 days after the vaccine/placebo administration.

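### Sections 6.4 and 8.2.9 disagree on whether the 3-day diary covers local reactions; under 8.2.9 there is no same-day participant record of their grade, size or duration

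*Combined protocol and SAP*

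**What the plan says.** Section 6.4 (Study Intervention Compliance) describes a "daily diary of solicited AEs for both local and systemic symptoms for 3 days" after the injection.

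Section 8.2.9 (Post Vaccination Symptom Log) describes the form participants take home. It is something "to use as a memory aid for tracking adverse events that occur during the 3 days following the injection", and its content is given as "Participants will record daily temperature and systemic symptoms". The section then says "solicited AEs occurring during the 3 days after the vaccine/placebo injection will include" six items: tiredness or feeling unwell, muscle aches, headache, chills, nausea and joint pain. None concerns the injection site. Temperature has its own instructions: at least one reading a day from Day 0 through Day 3, keeping the highest.

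Section 8.2.10 adds staff questions at about 48 hours and at Day 7, covering nine local items (Table 9) and fifteen systemic items (Table 10).

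Section 2.3.1 says local and systemic reactions can occur, "with most appearing within the first 24 hours and usually subsiding within" 48 to 72 hours.

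**The concern.** Both sections are current text, and a log cannot follow both as written. If it follows 8.2.9, participants make no daily note of local reactions, which are among the events Section 2.3.1 anticipates.

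The missing record matters for three reasons.

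- Section 8.3.4 grades erythema/redness and induration/swelling partly by size, with cut-offs at 2.5, 5 and 10 cm in diameter or the matching areas. A reaction that grows and fades between contacts is hard to grade afterwards.
- Section 8.3.4 also requires injection reactions of any grade to be entered in the database, and related events of Grade 1 or higher form the secondary safety endpoint.
- Grade 3 or higher injection-site reactions are events of special interest (8.3.7). If related and within 28 days, they also count towards the primary endpoint.

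Safety is the primary objective, with seven participants per vaccine arm, so the completeness of each participant's reactogenicity record matters.

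**Working it through.** No figure in the plan is in dispute. The check sets the passages side by side.

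**1. Local items.** Table 9 has nine: erythema, pruritus, tenderness, swelling, warmth, discoloration, pain, skin damage and induration. Section 8.2.9 names none of them.

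**2. Systemic items.** Table 10 has fifteen. The 8.2.9 list plus temperature matches seven: fatigue, malaise, headache, temperature, chills, nausea and myalgia. That leaves 15 − 7 = 8 not named: vomiting, flu-like symptoms, sweating, diarrhea, dizziness, anorexia, abdominal pain and syncope. In the other direction, 8.2.9 has joint pain, which Table 10 lacks.

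**3. What captures local reactions if 8.2.9 is followed.**

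| Time | Route | What it gives |
|---|---|---|
| Day 0 | 60 minutes of observation, site checked four times (8.2.8) | Direct inspection, ending before many reactions within a 24-hour onset window would have developed |
| From discharge | Instruction to contact the coordinator at once with site concerns (8.2.8) | Depends on the participant calling |
| Day 1 | Contact with every participant, by an agreed method (8.2.8) | General signs and symptoms; no local checklist named |
| About 48 hours | Table 9 questions (8.2.10) | All nine local items, prompted |
| Within 72 hours of onset | Evaluation of self-reported reactions above mild (8.2.10) | Not required if the reaction is improving or has gone |
| Day 7 | Table 9 questions (8.2.10) | All nine local items, prompted |

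The Day 1 and 48-hour contacts fall inside the expected window of onset within 24 hours and resolution by 48 to 72 hours. Local reactions are therefore asked about while many would still be present. No row yields a daily written entry of grade, size or duration by the participant, and no passage asks participants to measure a reaction.

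**4. Is Day 2 in person?** Section 8.2.8 calls Day 2 a visit, but it uses the same word for Days 84 and 168, which it says are by phone. Table 11 gives 0 mL of blood at Day 2, as at Days 84 and 168. In the text copy of the Schedule of Events read for this review, the telephone row has three marks, apparently under Days 0, 70 and 84. Moving them one column right gives Days 2, 84 and 168, which agrees with 8.2.8 for the last two. This points to a telephone contact at Day 2, but a misaligned table cannot settle it. If Day 2 is by telephone, no scheduled inspection of the site falls between the 60-minute observation and Day 7.

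**5. Illustration of sensitivity only.** The plan's exact one-sided 95% upper limits (9.2.1) reproduce:

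- 0 of 7: 1 − 0.05^(1/7) = 34.8%, stated as 35%.
- 1 of 7: the p solving (1 − p)^7 + 7p(1 − p)^6 = 0.05 is 52.1%, stated as 52%.

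One event more or fewer in an arm moves the limit by about 17 points. This shows how much one event weighs. It says nothing about whether one would be missed.

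**The case against.** The strongest reply is that the protocol already looks for local reactions repeatedly and near the time they are expected: direct observation, a contact the next day, all nine local items at about 48 hours and again at Day 7, and a route for evaluating anything above mild. This stands. A reader might infer from 8.2.9 that peak size would never be measured, or that there is a blind gap of about four days from resolution to Day 7. The documents support neither. The Day 1 and Day 2 contacts come before the expected end of most reactions, a participant may report or be evaluated at any point, and the protocol does not say when local reactions peak.

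Size is also only part of the grading. The cut-offs apply to redness and swelling, not to pain, tenderness, itching or warmth. Section 8.3.4 ties redness and swelling to interference with usual activities, which questions can elicit, and Grade 3 can be reached through ulceration, infection, abscess or drainage. This stands too, and is why the point is limited to grading that is partly by size.

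A missed Grade 3 reaction would have to escape several prompts. Section 2.2.4 reports that injection-site events in HIV-CORE 001 were all mild or moderate, and that Grade 3 events with the earlier vaccine occurred in under 5% of vaccinees. The effect on the primary endpoint is therefore less plausible than on the secondary one.

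Finally, the form itself is not in the documents. The six items in 8.2.9 may not be exhaustive, and the printed log may already follow 6.4. That could remove the practical gap, but not the need to reconcile the text.

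**Conclusion.** The conflict between 6.4 and 8.2.9 is certain on the text, as is the mismatch between the 8.2.9 list and Table 10. The consequence is modest and conditional. If the log follows 8.2.9, maximum grade and duration of local reactions rest on staff contacts and on what participants recall or volunteer between them, and may be under-recorded. The main exposure is the secondary Grade 1 or higher endpoint. The gap is wider if Day 2 is a telephone contact, which is likely but not established.

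The amount of under-recording cannot be estimated from the documents. The 52% and 35% limits should not be read as a forecast of bias in the primary endpoint: they show only what one event does to an arm of seven, and nothing in the plan makes a missed Grade 3 reaction likely.

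**What to change.** Bring 8.2.9 into line with 6.4:

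1. Add daily injection-site pain/tenderness, redness and swelling/induration to the existing Day 0 to 3 log, with the largest diameter of redness and swelling measured by a supplied ruler.
2. Align the systemic items in the log with Table 10, including a decision on joint pain, which appears only in 8.2.9.
3. State in 8.2.8 and the Schedule of Events whether Day 2 is in person or by telephone.

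The cost is a revised log page, a ruler per participant and slightly more daily effort for participants. No visit or sample is added. If the printed log already carries local items, correcting the wording of 8.2.9 may settle the first step, provided size is recorded.

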8.3 Adverse Events and Serious Adverse Events

8.3.1 *Definition of Adverse Events (AE)*

Adverse event means any untoward medical occurrence associated with the use of an intervention in humans, whether or not considered intervention-related (21 CFR 312.32 (a)).

An adverse event can therefore be any unfavorable and unintended sign (including an abnormal laboratory finding, for example), symptom, or disease temporally associated with the use of a medicinal product, whether or not considered related to the medicinal product. This includes any occurrence that is new in onset or aggravated in severity or frequency from the baseline condition, or abnormal results of diagnostic procedures, including laboratory test abnormalities.

Definition of Serious Adverse Events (SAE)

An adverse event (AE) or suspected adverse reaction is considered "serious" if, in the view of either the investigator or sponsor, it results in any of the following outcomes:

- death,
- a life-threatening adverse event,
- inpatient hospitalization or prolongation of existing hospitalization,
- a persistent or significant incapacity or substantial disruption of the ability to conduct normal life functions, or
- a congenital anomaly/birth defect.

Important medical events that may not result in death, be life-threatening, or require hospitalization may be considered serious when, based upon appropriate medical judgment, they may jeopardize the participant and may require medical or surgical intervention to prevent one of the outcomes listed in this definition. Examples of such medical events include allergic bronchospasm requiring intensive treatment in an emergency room or at home, blood dyscrasias, or convulsions that do not result in inpatient hospitalization, or the development of drug dependency or drug abuse.

